RESEARCH PROPOSAL

v1.2.11Nov2020

General Information

Principal Investigator: [name]
GW Medical Faculty Associates
Department of Anesthesiology and Critical Care Medicine,
[name]
[name]

Email: [contact]
Office: [contact]

Co-Investigators: [name]
Department of Anesthesiology and Critical Care Medicine
[contact]

[name]
Department of Anesthesiology and Critical Care Medicine
[contact]

[name]
Department of Surgery, Division of Transplantation
[contact]

Study Information

Study location: George Washington University Hospital
[name]
[name]

Study Title: Postoperative pain control with Systemic Lidocaine vs Regional Anesthesia in
Renal Transplant Patients

Study Type: Randomized trial

Study Duration: 36 months (Jan 2021 - Dec 2023)

Title: Postoperative Pain Control with Systemic Lidocaine vs Regional Anesthesia in Renal Transplant Patients

Background

GWU does about 75 kidney transplants a year. Adequate postoperative pain control is an important part of the patients' recovery. Renal transplant patients often have multiple comorbidities, that when combined with poorly controlled postoperative pain, can lead to tachycardia, hypertension, and increased risk of respiratory complications, which can in turn affect overall recovery and graft survival.

The use of patient-controlled analgesia (PCA) pumps is currently considered the standard of care in treating surgical pain in the immediate postoperative period [1]. Although a traditional mainstay of therapy, opioids have an unfavorable side effect profile that includes respiratory depression, nausea, postoperative ileus, sedation, and pruritus. Additionally, long-term opioid use is linked with opioid tolerance, addiction, and patient death. Patients that have high-level opioid use in the first year post-transplant have been found to have high rates of death and all-cause graft failure [2].

Recently, there has been a shift in post-operative pain management to utilize a multimodal approach of both non-pharmacologic and pharmacologic therapies. As a result, the use of other non-opioid therapies, such as lidocaine infusions and regional anesthetic techniques, like transverse abdominis plane blocks, have recently increased in popularity in perioperative pain management of renal transplant patients [3].

Intravenous lidocaine has an off label indication as analgesic and has good evidence for use in other areas such as colorectal surgery, trauma and orthopedics. Lidocaine infusions have a strong record of safety with relatively benign adverse side effects. Although data is promising, there is little established evidence of perioperative lidocaine infusions in renal transplant populations.

Transverse abdominis plane (TAP) blocks have emerged as a significant regional technique in the application of multimodal analgesia for abdominal surgeries. Historically, TAP catheters are avoided due to concern about infection near the operative site in immunosuppressed transplant patients. Establishing intravenous lidocaine as an effective treatment option will allow physicians to avoid the side effects of opioids and the infection risks of TAP catheter blocks.

Aims:

1. To see if Lidocaine infusion is non-inferior to TAP catheters for postoperative pain control
2. To see if higher rates of complications arise from non-opioid techniques (infection rates from TAP catheters, anesthetic toxicity from lidocaine infusion)

Recruitment: Recruitment for this study will take place in the preop waiting area. During that time, the purpose and method of the study will be explained to the patient. Patients will be informed of risks, benefits, and alternatives to participation in the study and will have the opportunity to sign consent after review of documentation and having all questions answered.

Recruitment cannot be done prior to the preop area because transplant surgeries are not scheduled far in advance. The organ recipient is called into the hospital when a match is found. The research team will be notified as soon as possible when a renal transplant is scheduled to allow for maximum amount of time to obtain consent.

Inclusion: Single Kidney transplant, >18 years old

Exclusion: Long term use of opioids (e.g. Chronic pain patients), history of substance abuse
Local anesthetic allergy
Complicated surgical course

- Intraoperative damage to other organs e.g. bowel

IRB NUMBER: NCR202221

IRB APPROVAL DATE: 02/18/2021

- Return to OR within 72 hours
- Postoperative ventilation

Methodology

Groupings

Patients will be randomly allocated into 2 groups: Lidocaine + PCA (L group) and TAP + PCA (T group). A member of the research team will perform the randomization and will notify the surgeon and the anesthesiologist on the case. This study is not blinded.

Sample size

The goal will be to recruit at least 55 patients for the Lidocaine group and 25 patients for the TAP block group for a total of 80 patients in all. Sample size for this study is based on information gained from a retrospective study of renal transplant patients. The aim is to demonstrate non-inferiority of lidocaine to TAP block where non-inferiority is defined as <10% difference in OME consumption (with a 95% confidence interval) between the groups.

Intervention

When a renal transplant case is posted to the OR schedule, the research team will be notified. A team member will then meet with the patient in the preop area to obtain informed consent. Once consent is obtained, the medical records of the patient will be screened for exclusion criteria. If the patient meets all criteria, they will be randomized to one of the two study groups.

The anesthesiologist and surgeon on the case will be informed immediately of the group assignment.

In addition to the treatments assigned to each group, all patients will receive the standard of care medications given pre-op, intra-op, and post-op. These medications include oral Tylenol, oral oxycodone as needed, IV morphine or hydromorphone as needed, ketamine as indicated, and Ondansetron as needed. All patients will receive a dilaudid PCA 0.5mg bolus Q10min postoperatively as standard of care.

Following the case, the research team will review the operative note and anesthesia postoperative note to identify any disqualifying surgical complications (injured bowel, patient remains intubated, complication requiring return to OR within 72 hours). If there are disqualifying complications, the anesthesiologist and the surgeon will be notified and the patient removed from the study. Any further treatment for postoperative pain will be per standard of care and the surgeon's discretion.

If there are no disqualifying surgical complications, the following orders for postoperative pain control will be placed per the patient's assigned group:

- Lidocaine (+PCA): 1.0-1.5 mg/kg/hour for 48 hours post-operatively.
- TAP (+PCA): 0.2% Ropivacaine at 6-10ml/hour for up to five days post-operatively.

Nursing will routinely record VAS scores for all patients per nursing standard of care.

The research team will review patient charts daily to obtain the VAS scores and total narcotics used at 12 hours, 24 hours, and 48 hours as well as any notes regarding complications.

Signs of complications due to the treatment methods will be reason to terminate the study and remove that patient from the study. Possible risks are listed below. The surgical team may terminate these treatment modalities as soon as a complication is identified, and may inform the research team as soon as possible afterwards.

Measures:

Demographics (age, gender, race, ASA)

Pain metrics at 12, 24, 48 hours (Time zero is arrival in PACU)

IRB NUMBER: NCR202221

IRB APPROVAL DATE: 02/18/2021

- Oral morphine Equivalents
- VAS score

Duration of operation

Surgeon

Length of stay (date of operation to date of discharge)

Complications

- Sepsis requiring antibiotic therapy
- Acute rejection of transplant
- Local Anesthetic Systemic Toxicity
- Need for CVVHDF
- Opioid toxicity requiring naloxone
- Ileus

Risks:

Risk of lidocaine infusion: Lidocaine toxicity (lightheadedness, dizziness, visual disturbances, confusion, tinnitus, and perioral numbness/peripheral paresthesia)

Risk of TAP block: local infection, hematoma, poor placement leading to inadequate pain control

Endpoints:

- VAS score
- Total opiate usage in morphine equivalents

Expected outcome and significance:

It is expected that patients with patients receiving lidocaine infusion will have equivalent opioid consumption and pain scores compared to patients receiving TAP blocks in the first 48 hours after surgery. If lidocaine infusion is demonstrated to be non-inferior to TAP blocks, this would provide physicians with an alternative to TAP blocks in controlling post-surgical pain while reducing total opioid usage.

Timetable: 36 months

References

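### Non-inferiority to TAP on a shared PCA background cannot show that lidocaine is effective over PCA alone or reduces opioid use, because no TAP effect is stated and the 10% margin is not tied to one

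*Combined protocol and SAP*

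**What the plan says.** Aim 1 is "To see if Lidocaine infusion is non-inferior to TAP catheters for postoperative pain control". Under Groupings, patients are randomised to lidocaine plus PCA or to TAP plus PCA; there is no third arm. The Intervention section gives both arms the same background: "All patients will receive a dilaudid PCA 0.5mg bolus Q10min postoperatively as standard of care", with oral oxycodone and intravenous opioid available as needed. Under Sample size, "non-inferiority is defined as <10% difference in OME consumption (with a 95% confidence interval) between the groups". No reason is given for 10%.

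Two passages go beyond the aim. The Background begins a sentence with "Establishing intravenous lidocaine as an effective treatment option will allow physicians to avoid the side effects of opioids and the infection risks of TAP catheter". Expected outcome and significance says that a non-inferior result would give physicians an alternative to TAP that controls pain and lowers total opioid consumption.

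On what TAP itself achieves, the text is qualitative. The Background calls it a significant technique in multimodal analgesia for abdominal surgery. The reference list includes a study of continuous TAP catheters in renal transplant and a meta-analysis of TAP. They are cited for PCA being standard care and for the growing use of non-opioid techniques, not for an effect size or the margin. The Risks section says poor placement of a TAP block can leave pain inadequately controlled.

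**The concern.** Being non-inferior to an active comparator implies being effective only if the comparator works in this setting by more than the margin. Here that means TAP must lower OME, relative to PCA alone, by more than 10% on the margin's own scale. Without that knowledge, similar OME in the two arms fits two explanations equally well: both add-ons spare opioid, or neither adds anything to PCA.

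The claim of reduced opioid use has a further difficulty. The same paragraph expects opioid consumption equal to that with TAP, so the reduction must be against something else, presumably PCA alone, and the trial does not contain that comparison.

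At stake is the published conclusion. A positive result could be presented as proof that lidocaine works and spares opioid, for an infusion with its own listed toxicity risks, when neither was tested.

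**Working it through.** **Inputs from the documents.** 55 lidocaine and 25 TAP patients, total 80; margin 10% of OME; 95% confidence interval (all under Sample size). No mean, SD, power or assumed difference is given, and no TAP effect.

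**The plan's own figure.** N = 80 cannot be reproduced without an SD and a power. Solving backwards with true difference 0, one-sided 0.025 and 80% power, the coefficient of variation (CV) of OME that fits 25/55 is 0.10 / [√(1/25 + 1/55) × (1.960 + 0.842)] = 0.10 / (0.2412 × 2.802) = 0.148. This only shows that 0.15 is near the value at which the trial would be adequately powered; the true CV is unknown.

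**When an inert infusion lies inside the margin.** Let e be the fraction of OME that TAP saves against PCA alone. Patients on an inert infusion use what PCA-alone patients use, so their true ratio to TAP is 1/(1 − e):

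- e = 5%: 1/0.95 = 1.053
- e = 9%: 1/0.91 = 1.099
- e = 10%: 1/0.90 = 1.111
- e = 20%: 1/0.80 = 1.250

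The plan does not say what the 10% is a percentage of. As a ratio to TAP, the threshold is e = 1 − 1/1.10 = 9.1%. Relative to the lidocaine arm, the difference is [1 − (1 − e)]/1 = e, so the threshold is 10%.

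**How often an inert infusion would be declared non-inferior.** Lying inside the margin is not the same as passing, because the confidence limit must also clear it. With the margin as 10% of the TAP mean, d = 1/(1 − e) − 1, and a normal approximation, the pass probability is Φ[(0.10 − d)/(CV × 0.2412) − 1.96]. CV and e are assumptions, shown as ranges:

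| TAP saving e | d | CV 0.15 | CV 0.30 | CV 0.50 |
|---|---|---|---|---|
| 0% | 0.000 | 79% | 28% | 13% |
| 2% | 0.020 | 59% | 19% | 10% |
| 5% | 0.053 | 26% | 10% | 6% |
| 9.1% | 0.100 | 2.5% | 2.5% | 2.5% |
| 15% | 0.176 | about 0% | 0.1% | 0.5% |

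Example, e = 0 and CV 0.15: 0.10/(0.15 × 0.2412) − 1.96 = 2.76 − 1.96 = 0.80, and Φ(0.80) = 79%. The first row is also the trial's power for an infusion truly equal to TAP: when TAP adds nothing, the test cannot separate the two cases. From e = 9.1% upwards the rule holds an inert infusion to 2.5% or less.

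**The case against.** The strongest reply is that the trial asks whether lidocaine can replace TAP on a common PCA background. That question is useful in itself, and two-arm active-control trials commonly lack an untreated arm. Aim 1 is worded in just those terms, and the Background sentence is motivation, not a decision rule. This stands: the aim and the comparison are not at fault. It does not rescue Expected outcome and significance, which draws the opioid-reduction conclusion directly from non-inferiority.

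Three stronger readings are tempting, and the documents do not support them.

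- A reader might infer that an inert infusion would pass. It would pass only as often as precision allows: even with e = 0, between 79% and 13% over the CVs shown. If TAP saves 9.1% or more, the margin does screen it out.
- A reader might infer from "Historically, TAP catheters are avoided due to concern about infection near the operative site in immunosuppressed transplant patients" that TAP is known to work poorly here. The reason given is infection, not weak analgesia. Two TAP papers are listed, though their results are not used in the plan.
- A reader might infer that the sponsor already has the data to settle the matter. The plan says only "Sample size for this study is based on information gained from a retrospective study of renal transplant patients". It does not say whose study it was, whether its data are at hand, or whether it had a PCA-alone group.

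**Conclusion.** The point holds as a limit on the conclusion. Followed exactly, the plan can show that opioid requirement with lidocaine is less than 10% above that with TAP. It cannot show that lidocaine adds to PCA or reduces opioid use. The gap matters if TAP's true saving is below about 9.1% of OME with the margin as a ratio to TAP, or below 10% relative to the lidocaine arm. The documents give no value for that saving, so these are thresholds, not estimates of how likely the problem is. The thresholds need only the definition of an inert infusion as equal to PCA alone. The pass rates also assume a one-sided 0.025 test of whether lidocaine is worse, a common SD expressed as a fraction of the TAP mean, and the CVs shown.

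**What to change.** In the Background and in Expected outcome and significance, limit what a positive result would mean to: *opioid requirement less than 10% above TAP on a common PCA background; efficacy or opioid reduction versus PCA alone not tested*. Delete the closing clause of Expected outcome and significance that claims lower total opioid use, and replace the Background's description of lidocaine as established to be effective.

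Keep the broader claim only if the retrospective study behind the sample size turns out to contain a PCA-alone group and shows a TAP effect whose lower confidence limit exceeds the margin on the same scale. That is a PCA-alone to TAP ratio above 1.10 (a saving above 9.1%) if the margin is a ratio to TAP, or a saving above 10% if it is relative to the lidocaine arm. In that case, state the effect, its source and the scale in the Sample size section, and say that the claim assumes the same TAP effect in this trial.

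The rewording costs nothing in patients, arms or treatment. The downside is a narrower claim.

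### The only non-inferiority rule is on opioid use: meeting it does not by itself establish non-inferior pain control, and it cannot support a claim of reduced opioid use

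*Combined protocol and SAP*

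**What the plan says.** Aim 1 is "To see if Lidocaine infusion is non-inferior to TAP catheters for postoperative pain control". The one numerical criterion is in Methodology, Sample size: "non-inferiority of lidocaine to TAP block where non-inferiority is defined as <10% difference in OME consumption (with a 95% confidence interval"). No other endpoint has a margin, test or success rule, and neither endpoint is named primary.

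OME and VAS are both listed in Measures, under "Pain metrics at 12, 24, 48 hours (Time zero is arrival in PACU"). Both are also listed under Endpoints, where the opioid endpoint reads "Total opiate usage in morphine equivalents". The Intervention section has the team collect "VAS scores and total narcotics used at 12 hours, 24 hours, and 48 hours". The Expected outcome and significance paragraph predicts that lidocaine patients "will have equivalent opioid consumption and pain scores compared to patients receiving TAP blocks in the first 48 hours after surgery". It then says that a non-inferior result would give physicians an "alternative to TAP blocks in controlling post-surgical pain while reducing total opioid usage".

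On the arms, Groupings says: "Patients will be randomly allocated into 2 groups: Lidocaine + PCA (L group) and TAP + PCA (T group"). There is no arm with PCA alone.

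**The concern.** The rule tests one quantity and the planned conclusions name two others.

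First, Aim 1 and the significance paragraph are about pain control. The plan itself treats pain as two measures, since it expects both opioid use and pain scores to be equivalent, but it decides on opioid use alone. A trial with OME inside the margin and clearly worse pain scores would meet the rule, and the significance paragraph would then offer lidocaine for controlling pain.

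Second, that paragraph attaches an opioid reduction to a non-inferior result. Non-inferiority to TAP with a 10% margin is compatible with no reduction, or with a small increase. If the reduction is meant against opioid-only care, the trial has no such comparator.

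What is at stake is the wording of the headline result: two statements could be published on the strength of a rule that tests neither.

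**Working it through.** **Logic, which needs no numbers**

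| Statement in the plan | What a met OME rule shows |
|---|---|
| Pain control is non-inferior (Aims; significance paragraph) | Lidocaine patients do not need more than 10% extra opioid. VAS can take any value. |
| Opioid use is reduced, versus TAP | The upper confidence limit is below +10%. It may lie above zero. |
| Opioid use is reduced, versus opioid-only care | Nothing. Both arms have PCA plus an active technique. |

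OME is indirect here for reasons in the Intervention and Groupings sections. Acetaminophen, and ketamine when indicated, are given alongside and do not count towards OME, and the study is open label. Equal OME therefore does not force equal pain.

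**The plan's own figure.** 55 + 25 = 80 adds up. The sample size cannot be reproduced, because no mean, SD, power or dropout is given. The point does not depend on it.

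**Illustration of size.** From the plan: 55 and 25 patients, 95% CI (taken as two-sided), margin 10%. Assumed, because the documents give none: OME lognormal with coefficient of variation (CV) 0.15, 0.3 or 0.5; patient-level OME-VAS correlation 0 to 0.7; VAS truly worse by 0.5 or 0.3 SD.

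1. k = sqrt(1/55 + 1/25) = 0.2412. With 78 df, t = 1.991, so the CI half-width is 1.991 × 0.2412 = 0.480 SD.
2. SD of log OME = sqrt(ln(1 + CV²)) = 0.149, 0.294, 0.472.
3. P(upper limit of the lidocaine/TAP ratio < m) at true ratio r = P(T < −1.991), where T is noncentral t with 78 df and noncentrality (ln r − ln m)/(SD × k). For r = 1.00 and m = 1.10 the noncentrality is −2.65, −1.35 and −0.84, giving pass rates of **74.4%, 26.4% and 12.8%**.
4. VAS alone: the chance that its 95% CI lies wholly on the worse side is 53.5% at 0.5 SD (noncentrality 0.5/0.2412 = 2.07) and 23.2% at 0.3 SD (1.24).
5. Both together, equal OME. At correlation 0 the results are nearly independent, so the joint share is about the product, for example 0.744 × 0.535 = 0.398. Other correlations come from simulation (400,000 draws each).

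| Share of all trials meeting the OME rule with a VAS CI wholly worse (correlation 0.7 to 0) | CV 0.15 | CV 0.3 | CV 0.5 |
|---|---|---|---|
| VAS worse by 0.5 SD | 31-40% | 5-14% | 1-7% |
| VAS worse by 0.3 SD | 9-17% | 1-6% | 0.1-3% |

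6. Reduction versus TAP. At a true ratio of 1.00 the upper limit is below 1.00 in 2.5% of trials. Passes with no reduction shown are therefore 74.4 − 2.5 = 71.9%, 26.4 − 2.5 = 23.9% and 12.8 − 2.5 = 10.3% of trials, or 97%, 91% and 81% of passes. At a true ratio of 0.85 the pass rates are 100%, 94.9% and 60.8%, and 99%, 65% and 48% of passes also have an upper limit below 1.00. The interval can show a reduction when there is one; meeting the 10% rule does not.

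**The case against.** Four replies have force.

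*OME is a legitimate choice.* The plan lists it as a pain metric. With on-demand PCA and as-needed opioids in both arms, opioid requirement reflects analgesic need. Aim 1 is a question, which the Sample size section makes operational through OME. This stands: putting the margin on OME is defensible. What does not follow is wording a met rule as non-inferior pain control.

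*VAS is not ignored.* It is a listed endpoint collected at three times, and nothing says that a poor result would go unreported. A reader might infer that pain scores will be disregarded; the documents do not support that. The gap is that VAS has no part in the criterion on which non-inferiority is declared.

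*The reduction clause is rationale, not a hypothesis.* Its comparator is unstated, and the Background sets these techniques against opioid-based care. That is a fair reading, and it makes the remedy an edit. The sentence is nonetheless conditional on this trial showing non-inferiority, and neither comparator supports it.

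*The illustrations depend on chosen inputs.* This also stands. The 97%, 91% and 81% apply only if true use is equal. The VAS conflict shrinks sharply at 0.3 SD. The correlation range of 0 to 0.7 is not a bound, since negative values would raise the shares.

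A reader might also take the phrase about a difference under 10% literally, so that lidocaine would fail for using over 10% less opioid. The same sentence speaks of non-inferiority of lidocaine to TAP, so that reading is strained and calls only for clearer wording.

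**Conclusion.** The point holds in a limited form. Meeting the OME rule supports non-inferior opioid requirement over the window analysed. It does not by itself establish Aim 1's non-inferior pain control, and it does not support a reduction in opioid use against TAP or against opioid-only care. These conclusions rest on the text alone.

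The size is illustrative, because OME variability, the OME-VAS correlation and the VAS effect are all assumed. Under equal OME, the share of trials meeting the rule with clearly worse VAS runs from 0.1% to 40% across the scenarios shown. The documents do not support saying that such a conflict is common, that OME is an invalid endpoint, or that the trial could never show a reduction versus TAP: an upper limit below 1.00 would show one, but the plan states no such step.

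This should be corrected. The trial can run as designed; its conclusions need to match its rule.

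**What to change.** - **Rule.** State it one-sidedly: lidocaine is non-inferior to TAP for opioid requirement if the upper limit of the two-sided 95% CI for the lidocaine/TAP ratio of OME over 0-48 h from PACU arrival is below 1.10. The plan already implies this window and time zero.
- **Conclusion.** Word the formal conclusion from that rule as opioid requirement. Report the lidocaine-minus-TAP VAS differences at 12, 24 and 48 h with 95% CIs beside it, before any statement about pain control.
- **Reduction clause.** Delete it, or claim a reduction versus TAP only if the same upper limit is below 1.00, examined after non-inferiority is met. This fixed order on one interval needs no extra alpha. Make no claim against opioid-only care.
- **Optional.** To keep a formal pain-control claim, add a VAS criterion with a clinically justified margin fixed in advance. Its power cost cannot be calculated from the documents, which give no VAS SD or margin.

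Cost: no new data are needed. The real price is a narrower headline claim in a trial whose title is about pain control. The change does not raise the chance of meeting the rule, which with equal OME is 26% at CV 0.3 and 13% at CV 0.5 under the assumptions above.

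### Randomised patients are removed for events during or after surgery by a team that knows the arm; all of them should stay in follow-up and in the primary analysis

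*Combined protocol and SAP*

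**What the plan says.** The Intervention section sets this order of events. Before surgery, "A team member will then meet with the patient in the preop area to obtain informed consent". The records are then screened, and "If the patient meets all criteria, they will be randomized to one of the two study groups". Next, "The anesthesiologist and surgeon on the case will be informed immediately of the group assignment". Under Groupings, a research team member does the randomising and the trial is declared open-label.

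The Exclusion list includes three events under a complicated surgical course: "Intraoperative damage to other organs e.g. bowel", "Return to OR within 72 hours" and "Postoperative ventilation".

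After the case, the Intervention section has the research team read the operative and anesthesia notes for disqualifying events, given as "injured bowel, patient remains intubated, complication requiring return to OR within 72 hours". A patient with such an event leaves the study and returns to usual pain care. Orders for the assigned arm are placed only if no such event is found.

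The Sample size section says "The goal will be to recruit at least 55 patients for the Lidocaine group and 25 patients for the TAP block group". The document defines no analysis set, makes no intention-to-treat statement, provides no blinded or independent eligibility check, and gives no rule for replacing removed patients.

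**The concern.** Randomisation makes the two arms comparable as randomised. Here some patients leave after randomisation because of events that follow it. The clinicians who write the notes know the arm, and so does the team that reads them. If the chance of an event, or of its being judged disqualifying, differs by arm, the remaining patients are no longer a randomised comparison.

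The stakes are higher because the aim is non-inferiority within a 10% difference in opioid consumption. Selective loss of patients with difficult recoveries can move the estimate towards or away from that margin. The TAP arm is also small: one removal is 1/25 = 4% of that arm, against 1/55 = 1.8% of the lidocaine arm.

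**Working it through.** **Step 1. When each exclusion can be known.** Study orders follow the post-case note review (Intervention). Pain outcomes are taken at 12, 24 and 48 hours from PACU arrival (Measures). Lidocaine runs for 48 hours and ropivacaine for up to five days (Intervention).

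| Criterion | When known | Relative to study orders | Relative to last outcome (48 h) |
|---|---|---|---|
| Damage to other organs | During surgery | Before | Before |
| Ventilation, read as still intubated after the case | End of surgery | Before | Before |
| Ventilation, read without a time limit | Any time after surgery | Can be after | During or after |
| Return to the operating room | Up to 72 h | Can be after | Up to 72 − 48 = 24 h after |

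The last row assumes that the 72-hour clock starts at about PACU arrival; its start is not stated. None of the events is known at randomisation. A return between 48 and 72 hours falls after the lidocaine infusion and all pain outcomes, while a TAP infusion may still be running. That patient could have complete data and still be removed. Nor can the operative and anesthesia notes read after the case show a return that has not yet happened, so the condition for placing orders and the 72-hour criterion do not fit together as written.

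**Step 2. The two lists.** The Exclusion list covers damage to other organs, with bowel as an example, and ventilation with no time limit. The Intervention list names bowel injury and a patient still intubated. Read literally, a bladder injury, or ventilation resumed on day 1, is excluded by one list and kept by the other. The second list may be shorthand for the first, but nothing says which governs.

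**Step 3. The planned size.** The figure of 55 + 25 cannot be reproduced, because power, SD and mean opioid consumption are not given. Working backwards, assume a margin of 10% of the TAP mean, no true difference, one-sided alpha 0.025 and 80% power. The SD-to-mean ratio that this size supports is then

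0.10 / [(1.960 + 0.842) × √(1/25 + 1/55)] = 0.10 / (2.802 × 0.2412) = 0.148.

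**Step 4. Effect of removals.** The document gives no removal rate. Assume a share d, equal in both arms, with exactly 80 recruited.

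- Remaining: 55(1 − d) and 25(1 − d).
- Information at 10%: 55 × 25/80 = 17.19 falls to 49.5 × 22.5/72 = 15.47, which is 10% less.
- Confidence interval width: multiplied by 1/√(1 − d).
- Power, if 80% with nobody removed: Φ(2.802 × √(1 − d) − 1.960).
- Recruitment that keeps 55 + 25 evaluable: 55/(1 − d) and 25/(1 − d), rounded up.

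| d (assumed) | Removed of 80 | Remaining | CI wider by | Power | Recruit instead |
|---|---|---|---|---|---|
| 5% | 4 | 52.2 + 23.8 | 2.6% | 78.0% | 58 + 27 = 85 |
| 10% | 8 | 49.5 + 22.5 | 5.4% | 75.7% | 62 + 28 = 90 |
| 15% | 12 | 46.8 + 21.2 | 8.5% | 73.3% | 65 + 30 = 95 |

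About 75 transplants a year (Background) over 36 months is 75 × 3 = 225 before consent and exclusions, so these totals are not ruled out by volume.

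**The case against.** The best defence is that the plan describes an open two-stage screen: a chart check before surgery, then a check of the surgical course afterwards. A reader might infer that the condition for randomisation can never be met. The text does not support that, because the sentence follows a records screen and can be taken to mean what a preoperative chart shows. This part of the defence stands.

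It also stands that bowel injury and continued intubation are fairly objective and are found before either arm's orders are placed, so removal for them does far less harm than removal during treatment. It does not answer the return within 72 hours, or ventilation read without a time limit.

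On numbers, the recruitment goal is a minimum, so the team may recruit more. A reader might infer that the trial must fall short of 55 + 25; no removal rate is given, so that cannot be concluded. However, no rule says that the goal counts evaluable patients, and extra recruits do not undo selective removal.

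A reader might also infer that patients are selected out on a study outcome, since the Background links poor pain control to respiratory complications. Ventilation is not among the listed endpoints or complications, and the link depends on the untimed reading. Likewise, the two lists may be one list in shorthand, so a definite contradiction on organ injury is not shown.

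**Conclusion.** The concern holds in this form: patients are randomised before surgery with the arm disclosed, then removed for later events by an unblinded team, and no analysis set protects the comparison. The order of events is explicit in the text. Bias is a risk, not a demonstrated effect. It is limited for organ injury and continued intubation, and more serious for a return within 72 hours, where removal can depend on the arm and can discard complete data.

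The numerical loss is secondary and unknown. Under the assumed 5 to 15%, the confidence interval widens by about 3 to 8%. The power figures also rest on the assumption that 55 + 25 would give exactly 80%.

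A reader might conclude that assignment must move to the end of surgery. The document does not say when the TAP catheter is inserted, so feasibility is not established, and a later assignment would not address the return within 72 hours.

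**What to change.** 1. Reword the removal rule so that stopping study treatment is separate from leaving the study.
2. Continue the chart-based collection of oral morphine equivalents and VAS to 48 hours for every randomised patient, and state how a VAS score that cannot be obtained will be handled.
3. Make all randomised patients, in their assigned arms, the primary analysis set. Report the set omitting disqualified patients alongside it, because this is a non-inferiority comparison, and state in advance how a disagreement between the two will be read.
4. Report disqualifications by arm and reason.
5. Reconcile the Exclusion and Intervention lists, including the time limit on ventilation and how the 72-hour criterion fits with orders placed after the case. Which clinical rule applies is for the investigators to decide.
6. As an option, if the timing of catheter insertion allows, open the assignment after the end-of-surgery check. That would also avoid post-randomisation loss from organ injury and continued intubation, but someone must be available to assign at that point.

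Items 1 to 5 cost a protocol amendment and chart review for a few more patients, with no added recruitment. The downside is that some patients who did not receive their assigned treatment stay in the primary analysis and may dilute the difference. Dilution can favour a non-inferiority claim, which is why the second set is needed.
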